14.3 Expedited Reporting Requirements

Expedited reporting will be conducted in accordance with FHCC/Cancer Consortium IRB policies, FDA regulations, and agreements with Seattle Genetics. Reportable events and required time frames include:

Individual expedited SAE reports required by competent health authority (i.e. FDA, Health Canada)	At time of submission to competent authority: Seattle Genetics Drug Safety by: [contact] or [contact] (USA only toll free) Email: [contact]
Cumulative aggregate listing of all SAEs	Monthly: [contact] or portal

Reporting Timeframe: The Sponsor-Investigator will report all Serious Adverse Event (SAE)s that occur in a study subject within the following timeframe:

- SAEs/Suspected Adverse Reactions that are *fatal or life-threatening*, will be reported to the FDA as an IND Safety Report (via narrative report or MedWatch form 3500A) within 7 calendar days of the Sponsor-Investigator's awareness of the event including assessment of causality to the Product. Notification to the FDA will be submitted concurrently to Seattle Genetics.
- SAEs/Suspected Adverse Reactions that are *unexpected*, will be reported to the FDA as an IND Safety Report (via narrative report or MedWatch form 3500A) within 15 calendar days of the Sponsor-Investigator's awareness of the event including assessment of causality to the Product. Notification to the FDA will be submitted concurrently to Seattle Genetics.
- AEs that are *unexpected, possibly, probably or definitely related to the study drug*, and *serious or suggest a risk of greater harm from the research than previously known* will be reported to the IRB within 10 calendar days of the Sponsor-Investigator's awareness of the event.
- **Reporting Period:** The reportable events that are subject to this provision are those that occur from the start of administration of the first dose of the

Product through thirty (30) days after discontinuation of the Product. SAEs occurring more than thirty (30) days after discontinuation of the Product that are assessed by the Sponsor-Investigator as related to the Product should also be reported.

- **Pregnancy Reporting Requirements:** Based on the estimated date of conception, all pregnancies that occur from time of informed consent to within 30 days of last study drug dose, including any pregnancies that occur in the partner of a male study patient, are required to be reported to SGI within 7 days of becoming aware of such pregnancy. At the time of reporting SGI will provide the Sponsor-Investigator a Pregnancy Reporting form for collecting information. All pregnancies that occur during this time period will be monitored for the full duration; all perinatal and neonatal outcomes should be reported. Infants should be followed for a minimum of 8 weeks.

Initial reporting will occur in the time frames noted above. The Sponsor-Investigator will assist Seattle Genetics in investigating any SAE and will provide any follow-up information reasonably requested by Seattle Genetics.

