5.2 Exclusion Criteria

5.2.1. Prior transplant within 100 days.

- 5.2.2. Radioimmunotherapy within 12 weeks.
- 5.2.3. Known HIV or hepatitis B positivity or prior PML.
- 5.2.4. Active infection or other medical condition which would preclude treatment in the opinion of the principal investigator. This would include a corrected DLCO of <60% predicted or symptomatic interstitial lung disease.
- 5.2.5. ECOG performance status >2.
- 5.2.6. Known active CNS involvement.
- 5.2.7. Peripheral neuropathy >Grade 1 if due to brentuximab vedotin or any peripheral neuropathy >Grade 2.
- 5.2.8. Intolerance to brentuximab vedotin.
- 5.2.9. Concurrent use of other anti-cancer agents or experimental treatments.
- 5.2.10. No current or prior autoimmune disease with the exception of vitiligo and autoimmune alopecia (Arm B only).
- 5.2.11. Pregnancy or breastfeeding. (Females of childbearing potential must have a negative serum or urine beta human chorionic gonadotropin (β -hCG) pregnancy test result within 7 days prior to the first dose of brentuximab vedotin. Females with false positive results and documented verification that the patient is not pregnant are eligible for participation. Females of non-childbearing potential are those who are postmenopausal greater than 1 year or who have had a bilateral tubal ligation or hysterectomy. Females of childbearing potential and males who have partners of childbearing potential must agree to use 2 effective contraceptive methods during the study and for 6 months following the last dose of brentuximab vedotin or 6 months following the last dose of nivolumab, whichever is later.)

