7.0 TREATMENT PLAN

- 7.1 For treatment or dose modification related questions, please contact [name] at [contact]. Dose adjustment of nivolumab may follow the US package insert (opdivo.com)

- 7.2 Each cycle of therapy is given every 21 days. Up to 4 cycles of chemotherapy will be administered on protocol. Following protocol therapy, patients may go on to receive other therapy at the discretion of their physician. Brentuximab vedotin will no longer be supplied by the study.

ARM B (Open to Accrual)				
EACH CYCLE (UP TO 4 CYCLES TOTAL)				
Chemotherapy	Treatment Day (Actual treatment dates may vary up to +/- 2 days)			
	Cycle 1	Cycle 2	Cycle 3	Cycle 4
	Day 1	Day 1	Day 1	Day 1
Brentuximab vedotin 1.8mg/kg (maximum 180 mg) over approximately 30 minutes	X	X	X	X
Nivolumab 3 mg/kg	X	X	X	X

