14.2 Adverse Event Monitoring

AEs of Grade 3 and above, and SAEs occurring at any grade will be monitored and recorded in study-specific case report forms (CRFs) from the time of study enrollment through 30 days following the end of study treatment or 100 days after the last dose of nivolumab whichever is later or until the patient receives an alternative anti-cancer therapy.. AEs related to lymph node (tumor) biopsies

that are done solely for research study screening purposes will be monitored, recorded, and reported according to the same standards, with the exception that assessment of study drug attribution will be excluded from reporting criteria.

The Sponsor-Investigator will assess AE grading, attribution, and expectedness.

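### Mandatory pregnancy reporting and follow-up stop at conceptions 30 days after the last dose, while contraception is required for 6 months, leaving about 84% of the post-dose contraception period without that duty

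*Combined protocol and SAP*

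**What the plan says.** Two sections set time limits that concern conception.

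- **Section 5.2.11 (exclusion criteria).** Women of childbearing potential, and men whose partners are, "must agree to use 2 effective contraceptive methods during the study and for 6 months following the last dose of brentuximab vedotin". For the second drug the limit is "6 months following the last dose of nivolumab, whichever is later".
- **Section 14.3 (Pregnancy Reporting Requirements).** The supplier must be told within 7 days of "all pregnancies that occur from time of informed consent to within 30 days of last study drug dose". The date that counts is set by the words "Based on the estimated date of conception". Partners fall under the same limit: "including any pregnancies that occur in the partner of a male study patient". So does follow-up to outcome: "All pregnancies that occur during this time period will be monitored for the full duration".

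No section extends pregnancy reporting beyond 30 days. Section 14.2 sets a longer window for recording adverse events, "30 days following the end of study treatment or 100 days after the last dose of nivolumab whichever is later", but does not mention pregnancy, and recording can end sooner if the patient starts another anti-cancer therapy.

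**The concern.** By requiring two methods for 6 months after the last dose, the protocol treats conception in that period as something to guard against. The protocol does not use the term risk period, but that is a fair reading of the rule. A conception after day 30 but within the 6 months is therefore one that the protocol tries to prevent, yet Section 14.3 requires neither a report nor follow-up of the mother and infant if it happens. Because conception date governs, a pregnancy conceived by day 30 and discovered later is covered. One conceived on day 31 is not.

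At stake is safety information on exposed pregnancies, in patients and in the partners of male patients. Section 13.3 anticipates 8 women and 12 men in Arm B, so the partner provision is not a side issue. The response-rate objective is not involved.

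**Working it through.** The plan gives no figure of its own to reproduce. The check is arithmetic on the windows.

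**Inputs**
- Pregnancy reporting and follow-up: consent to 30 days after the last study drug dose (14.3).
- Contraception: during the study and 6 months after the last dose of the later drug (5.2.11). Six months is taken as 183 days, with a range of 180 to 184 (assumption).
- Arm B schedule: "Each cycle of therapy is given every 21 days. Up to 4 cycles of chemotherapy will be administered on protocol" (7.2). The fourth dose falls 3 × 21 = 63 days after the first.
- Maximum delay: 4 weeks before a cycle (7.5.4, 8.1). With all of cycles 2 to 4 delayed, that is 3 × 28 = 84 days.
- Consent to first dose: 0 to 28 days (assumption).

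**Post-dose period**
- Uncovered days = 183 − 30 = 153.
- Uncovered share = 153 / 183 = 83.6%. Covered share = 30 / 183 = 16.4%.
- With 180 days: 150 / 180 = 83.3%. With 184 days: 154 / 184 = 83.7%. The length chosen for 6 months hardly matters.

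**Whole contraception period, Arm B**

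Uncovered share = 153 / (days from consent to first dose + days from first to last dose + 183).

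| Case | Total days | Covered | Uncovered | Uncovered share |
|---|---|---|---|---|
| From first dose, no delay | 63 + 183 = 246 | 63 + 30 = 93 | 153 | 62% |
| From consent (28 days), no delay | 274 | 121 | 153 | 56% |
| From first dose, maximum delays | 63 + 84 + 183 = 330 | 177 | 153 | 46% |
| From consent (28 days), maximum delays | 358 | 205 | 153 | 43% |

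The uncovered time is always 153 days. Only the denominator moves.

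**Do other clauses fill the gap?**
- Section 14.1 counts a congenital anomaly or birth defect as a serious adverse event, but does not list pregnancy itself.
- Section 14.3 asks for serious events later than 30 days after discontinuation if they are assessed as related. Its reporting duty concerns events in a study subject. A normal outcome, or a loss not classed as a related serious event, falls outside. A male patient's partner and her infant are not study subjects, so their coverage is doubtful.
- Even if the 100-day limit in 14.2 were applied to pregnancy, which the text does not do, 183 − 100 = 83 days (45%) would remain uncovered.

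**Which drug dates the window?** Section 14.3 refers to the last study drug dose without naming the drug, whereas 5.2.11 and 14.2 name nivolumab. Both drugs are scheduled on Day 1 of every Arm B cycle, so the dates differ only if one is stopped or omitted. This is a minor point.

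**The case against.** The strongest reply is that the two rules do different jobs. Section 5.2.11 is a precaution asked of patients, and the 14.3 clause is a duty to notify the drug supplier. A site can follow both, and nothing in the documents says that the windows must be equal. Section 14.3 also ties expedited reporting to IRB policies, FDA regulations and agreements with the supplier. These cannot be seen here; they may be where the 30 days comes from, and they may impose further duties. This stands: a reader might infer that the protocol contradicts itself, and it does not. The protocol gives no reason for the shorter window, however, and on its own text the gap is there.

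A reader might also infer that the trial would never learn of a pregnancy in months 2 to 6. The documents do not support that. The 30-day limit is a minimum and bars no later report. Late related serious events, which could include a birth defect, should be reported without an end date. The study calendar describes typical standard-of-care follow-up every 3 months in the first year, so patients are likely to be seen. What remains true is that nothing requires the pregnancy itself to be reported or followed.

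Finally, materiality is low. Arm A is closed and Arm B plans 20 patients. That limits the importance of the point but does not remove it, since each exposed pregnancy in so small a group carries information.

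**Conclusion.** The point holds as a misalignment of two windows. After the last dose, about 153 of 183 days (84%) of the required contraception period carry no duty to report or follow a pregnancy. This rests on taking 6 months as about 183 days and on reading 14.3 as written.

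The 84% must not be read as a share of the whole contraception period, which also includes time on study that 14.3 covers in full. On that basis the uncovered share in Arm B is 56% to 62% without delays and 43% to 46% with maximum delays. A reader might infer that most of the whole period is always uncovered; with long delays that is not so.

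The late serious-event clause narrows the gap without closing it. Few or no events are expected in 20 patients, and the response-rate analysis is unaffected. This is a cheap improvement to safety capture.

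**What to change.** Reconcile the two sections by amending one sentence in 14.3. Run pregnancy reporting and outcome follow-up, for patients and partners, to the end of the contraception period already stated in 5.2.11, dated from the last on-protocol dose of brentuximab vedotin or nivolumab, taking the later. Keep the 7-day reporting time and the existing outcome and infant follow-up.

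The limit to on-protocol doses is needed. Nivolumab comes from commercial supply (3.1), and patients may go on to other therapy after protocol treatment (7.2). Without the limit, off-study doses could extend the window indefinitely. Naming both drugs also settles which dose dates the window. The change takes no position on how long contraception should last and alters no dose or treatment rule.

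The cost is a one-sentence amendment, alignment with the supplier agreement, and follow-up of a rare extra pregnancy. The change adds no pregnancy test or visit. The calendar schedules pregnancy tests only at pre-entry, so later pregnancies would still come to light through standard-of-care contact.

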14.4 Routine Reporting Requirements

Routine reporting of adverse events will be conducted in accordance with FHCC/Cancer Consortium IRB policies, FDA regulations, and agreements with Seattle Genetics. This will include annual summary reporting of AEs to the IRB as per the requirements of the Continuation Review Report structure, and annual reporting of the most frequent and most serious AEs to the FDA as part of annual reporting to the IND under the provisions of 21 CFR 312.33. Annual reports to the FDA will be submitted concurrently to Seattle Genetics.

15.0 DATA AND SAFETY MONITORING PLAN

Ongoing trial oversight is carried out by the Principal Investigator and the study coordinator. These individuals will meet on a regular basis to review recently acquired data and adverse events. The data recorded within the research charts and protocol database is compared with the actual data that is available from the medical record and/or clinical histories. Data detailed in the research case report forms includes the nature and severity of all toxicities, which are also reported as described above.

Institutional support of trial monitoring is provided in accordance with the FHCC Institutional Data and Safety Monitoring Plan. Under the provisions of this plan, the FHCC Clinical Research Support office coordinates monitoring for data accuracy and compliance by consultants, contract research organizations, or FHCC employees unaffiliated with the conduct of the study. Independent monitoring visits occur at specified intervals determined by the assessed risk level of the study and the findings of previous visits. In addition, protocols are reviewed at least annually by the Data and Safety Monitoring Committee (DSMC) and the Institutional Review Board (IRB). The DSMC reviews accrual, adverse events, stopping rules, and adherence to the data and safety monitoring plan for studies actively enrolling or treating patients. The

FHCC/Cancer Consortium IRB reviews the study progress and safety information to assess continued acceptability of the risk-benefit ratio for human subjects. Approval of both committees as applicable is necessary to continue the study.

This protocol does not require a separate data safety monitoring board. The trial will comply with the standard guidelines set forth by the regulatory committees of the FHCC (Scientific Review Committee, IRB, DSMC) and other state and federal guidelines.

16.0 RECORDS

Research staff under the supervision of the investigators will maintain case report forms and secured databases on the relevant clinical and laboratory data. Records maintained in investigators' offices will be secured with access limited to study personnel. Authorization for access to medical records will be obtained from all patients in accordance with provisions of the Health Insurance Portability and Accountability Act (HIPAA).

17.0 REGULATORY RESPONSIBILITIES OF SPONSOR-INVESTIGATOR

The Sponsor-Investigator of the IND and protocol will ensure that the study is conducted in accordance with all applicable institutional, state, and federal regulatory requirements, including, but not limited to: compliance with requirements for IRB and other regulatory approvals, monitoring responsibilities, reporting obligations, and compliance with standards for written informed consent from all patients entering the study.

